4.1. Overall Design

Study AACN is a multicenter, randomized, open-label, head-to-head, Phase 3 study of donanemab compared to aducanumab in participants with early symptomatic AD.

Participants who meet entry criteria will be randomized in a 1:1 ratio to 1 of the following treatment groups:

- donanemab: 700 mg IV Q4W for first 3 doses and then 1400 mg IV Q4W
- aducanumab: refer to PI/routine clinical practice

The maximum total duration of study participation for each participant, including screening and the post-treatment follow-up periods, is up to 127 weeks:

- Lead-In: any time prior to complete screening
- Complete Screening: up to 7 weeks
- Open-label study period: 76 weeks
- Follow-Up: up to 44 weeks

The maximum duration of treatment is 72 weeks.

Scheduled Reduction of Donanemab

Participants randomized to donanemab whose amyloid plaque reduction as measured by florbetapir F18 PET scans at Visit 8 (Week 24) or Visit 15 (Week 52) meets criteria will stop donanemab infusions but continue all other assessments for the remaining duration of the open-label period and short-term follow-up period. These dose reduction rules are defined by the sponsor.

Participants randomized to aducanumab will continue monthly infusions throughout the open-label period, regardless of amyloid plaque reduction on florbetapir F18 PET scans.

Change in amyloid burden (as assessed with florbetapir F18 PET by personnel blinded to treatment allocation) will be compared in donanemab and aducanumab-treated participants.

Participant randomization will be stratified by amyloid burden and ApoE ϵ 4 status (noncarrier/heterozygous/homozygous).

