2.1. Multiplicity Adjustment

The statistical comparisons for the co-primary efficacy endpoints and the key secondary endpoints will be carried out such that strong control of Type I error will be achieved at a 2-sided level of 5%. Since both co-primary endpoints need to be met for the study to be successful, each of the co-primary endpoints will be tested at the full 2-sided significance level of 0.05. If both these co-primary endpoints are statistically significant at the 5% level, the key secondary endpoints will be tested in a gated manner in the following order at the 5% level:

- i) the mean change from baseline in amyloid plaque levels at 6 months
- ii) the mean change from baseline in amyloid plaque levels at 12 months
- iii) time to amyloid plaque clearance tested at the end of the study
- iv) the mean change from baseline in amyloid plaque levels at 18 months

When data for 6 months PET scans are available, the co-primary objectives will be assessed. If both these null hypotheses for the co-primary objectives are rejected, the mean change from baseline in amyloid plaque levels at 6 months will be compared between donanemab and aducanumab. If the null hypothesis is rejected for the 6-month comparison, the mean change comparison between donanemab and aducanumab will be assessed when 12-month PET scans are available. The next two key secondary endpoints (in order) are time to amyloid plaque clearance, and mean change from baseline in amyloid plaque levels at 18 months, which will be assessed at the end of the study when data for all time points are available.

The testing scheme will follow this gating pattern until all four key secondary hypotheses are tested or until the null hypothesis is not rejected for an endpoint, at which point, any further testing would stop for the key secondary objectives.

If an interim analysis is performed, the alpha spending approach specified in Section 4.9 will be followed to control the overall Type I error rate for the co-primaries under a two-sided level of 5%. The testing approach for the key secondary endpoints should an interim be performed will be similar as described in this section. However, the alpha available for testing the key secondary endpoints in the event an interim analysis is performed is described in Section 4.9.

3. Analysis Sets

For the purposes of analysis, the following analysis sets are defined:

Participant Analysis Set	Description

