4.1. General Considerations

Statistical analysis of this study will be the responsibility of the Sponsor or its designee.

Unless otherwise noted, tests of treatment effects will be conducted at a 2-sided alpha level of 0.05 (or equivalently, a 1-sided 0.025 alpha level); 2-sided CIs will be displayed with a 95% confidence level. If relevant, tests of interactions between treatment and other factors will be conducted at an alpha level of 0.05.

Participant assignment to treatment will be stratified by ApoE ϵ 4 genotype, and baseline amyloid level. These factors will be included in analysis models unless otherwise stated.

All amyloid plaque analyses will follow the ITT principle unless otherwise specified. An ITT analysis is an analysis of data by the groups to which participants are assigned by random allocation, even if the participant does not take the assigned treatment, does not receive the correct treatment, or otherwise does not follow the protocol.

When change from baseline is assessed, participants will be included in the analysis only if both a baseline and a postbaseline measure are available. Unless otherwise defined, a baseline measure is the last non-missing observation collected prior to the first administration of study medications. Endpoint is the last non-missing post-baseline measurement.

To allow for sequential testing, database locks and the testing of corresponding primary and key secondary objectives are expected to occur after all randomized participants have had a chance to complete the scheduled 24-week PET scan, the scheduled 52-week PET scan, and the scheduled 76-week PET scan. If an interim analysis occurs, a database lock will additionally occur after a sufficient number of participants (for example, approximately 75-125) have had a chance to complete the scheduled 24-week PET scan. Data collected during the immunogenicity and safety follow-up period will be summarized and analyzed separately.

Any change to the data analysis methods described in the protocol will require a protocol amendment only if it changes a principal feature of the protocol. Any other change to the data analysis methods described in the protocol, and the justification for making the change, will be described in the SAP and the clinical study report. Additional exploratory analyses of the data will be conducted as deemed appropriate.

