4.5.1.2. Main analytical approach

As there is only one post-baseline PET assessment within the first 6 months of the trial, mean change from baseline in amyloid plaque levels at Month 6 will be analyzed using an analysis of covariance model with the treatment group as fixed effect variable of interest, and APOE e4 genotype, baseline amyloid levels, and baseline age as the covariates. For the analysis of mean change from baseline at 12 and 18 months, a separate mixed model repeated measures (MMRM) analysis with data up to and including that specific time point will be used. This model will include the fixed effects of treatment, time, and treatment by time interaction, and APOE e4 genotype, and baseline amyloid level as covariates. Correlation among repeated measures on the same subject will be accounted for by enforcing an unstructured variance covariance matrix among the residuals. If the unstructured covariance structure matrix results in a lack of convergence, the following structures will be used in sequence until convergence is reached: heterogeneous Toeplitz covariance structure, heterogeneous autoregressive covariance structure,

heterogeneous compound symmetry covariance structure, and compound symmetry covariance structure. The Kenward-Roger approximation will be used to estimate the denominator degrees of freedom.

Time to amyloid plaque clearance between the two treatment groups will be analyzed and compared using a log-rank test for survival data. Kaplan-Meier estimates of percent of participants reaching amyloid plaque clearance and the p-value from the log-rank test will be used to determine the superiority of donanemab vs aducanumab in lowering time to plaque clearance.

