4.5.1.3. Sensitivity Analyses

Observed values for mean changes in centiloid values will be reported for 6-, 12-, and 18- month PET scans. Additionally, a last-observation-carried-forward (LOCF) mean change analysis in centiloid values will be reported.

Time to plaque clearance will also be analyzed using a Cox proportional-hazards model with the treatment group as fixed effect variable of interest, and APOE e4 genotype, baseline amyloid levels, and baseline age as covariates.

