If an interim analysis is performed and both co-primary endpoints/null hypotheses are rejected, the 2-sided alpha available to test the four key secondary endpoints will be at least as much as 0.03100566 yet will be lower than 0.05. The alpha level will be determined using the approach outlined in Hung, Wang, and O'Neill (2007). If an interim analysis is performed and we fail to reject both co-primary endpoints, the co-primary endpoints will be re-tested (when all patients have their 6 month PET scan) and key secondary endpoints will be tested in a sequential/gated manner at a 2-sided alpha level of 0.02774 as determined by the Pocock alpha spending approach. The order of testing and the gating strategy for the key-secondary endpoints will be the same as detailed in Section 2.1.

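### The log-rank test that decides time to clearance names no randomization strata; stratifying it would be a free, low-priority improvement to a valid but possibly conservative test

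*SAP*

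**What the plan says.** **The test.** SAP 4.5.1.2: "Time to amyloid plaque clearance between the two treatment groups will be analyzed and compared using a log-rank test for survival data". Protocol 9.3.4.2 names the same test; neither section names strata or covariates. SAP 4.5.1.2 rests the superiority conclusion on the Kaplan-Meier estimates and the log-rank p-value.

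**Randomization.** Protocol 4.1: "Participant randomization will be stratified by amyloid burden and ApoE" ε4 status (noncarrier, heterozygous, homozygous). SAP 4.1 agrees: "Participant assignment to treatment will be stratified by ApoE" ε4 genotype and baseline amyloid level. The number of amyloid levels and their cut-points are not given.

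**The general rule.** SAP 4.1 says of the two factors: "These factors will be included in analysis models unless otherwise stated". SAP 4.5.1.2 neither applies this to the log-rank test nor declares an exception.

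**The adjusted analysis.** SAP 4.5.1.3: "Time to plaque clearance will also be analyzed using a Cox proportional-hazards model with the treatment group as fixed effect variable of interest", with ApoE ε4 genotype, baseline amyloid and age as covariates. It is listed as a sensitivity analysis.

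**Place in the hierarchy.** SAP 2.1 puts this endpoint third of four key secondaries, as "time to amyloid plaque clearance tested at the end of the study", ahead of the 18-month mean change. Without an interim, "the key secondary endpoints will be tested in a gated manner in the following order at the 5% level". If an interim is held and not passed, SAP 4.9 says "key secondary endpoints will be tested in a sequential/gated manner at a 2-sided alpha level of 0.02774".

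**The concern.** The co-primary logistic model, the 6-month analysis of covariance and the 12- and 18-month repeated-measures models all include ApoE ε4 and baseline amyloid. The log-rank test is the only confirmatory analysis that does not.

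Two mechanisms make this potentially wasteful. First, stratified randomization balances the arms within strata. If the strata predict clearance, the pooled log-rank variance still counts between-stratum variation that the design has removed, so the statistic varies less than its formula assumes. Second, by month 6 the plan expects 35.7% of donanemab and 3.0% of aducanumab participants to have cleared. If those with low baseline amyloid clear first, the donanemab participants still at risk are enriched for high amyloid. Later unstratified comparisons then tilt against donanemab.

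At stake is some power for a gated test whose failure would also stop the 18-month mean-change test. The choice should be fixed before data are seen.

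**Working it through.** **1. The plan's own figure.** The SAP states at least 98% power for each co-primary comparison, and none for the log-rank test. Inputs: 35.7% v 3.0% at 6 months, about 90 per arm with a 6-month scan, about half with intermediate tau. Two-proportion formula, two-sided 0.05:

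power = Φ{[(p₁−p₂) − 1.96·√(2p̄(1−p̄)/n)] / √[(p₁(1−p₁)+p₂(1−p₂))/n]}

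With n = 45: p̄ = 0.1935; (0.327 − 1.96 × 0.0833)/0.0758 = 2.16, so power is 98.5%. With n = 90 it exceeds 99.9%. The stated figure reproduces.

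**2. Reference power for the log-rank test.** From the 18-month rates, HR = ln(1−0.546)/ln(1−0.278) = 2.42. Expected events with 100 per arm: 100 × (0.546 + 0.278) = 82.4. Schoenfeld: Φ(√(82.4/4) × ln 2.42 − 1.96) = Φ(2.06) = 98.0%. With 90 per arm (74 events) it is 96.8%. This is approximate, because the planned rates put most of the difference at 6 months.

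**3. Size of the conservatism.** The stratified statistic is Z = Σ(Oₛ−Eₛ)/√ΣVₛ over strata s; the unstratified one treats everyone as a single stratum. If the null SD of the unstratified Z is σ, its actual type I error is 2[1 − Φ(1.96/σ)]. Simulation with 90 per arm, 6 strata and clearance log-odds falling by 1.0 to 1.5 per SD of baseline amyloid (assumed) gives σ of 0.88 to 0.92. The formula then gives 0.026 to 0.033. The simulated rejection rates were 0.026 to 0.031 unstratified and 0.041 to 0.049 stratified.

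**4. Simulation at the planned rates.** From the documents: N = 200, 1:1, scans at 6, 12 and 18 months, 10% loss before month 6, and clearance rates of 35.7/50.1/54.6% v 3.0/22.8/27.8%, read as cumulative. Assumed: blocks of 4 within strata, 5% loss in each later interval, ApoE shares 30/53/17%, 2, 3 or 6 amyloid levels (6, 9 or 18 strata), and a clearance odds ratio between lowest and highest amyloid stratum of 1, 3 or 10 (ApoE odds ratio 1, 1.5 and 1.5 respectively). There were 8000 null and 5000 alternative runs. Each cell shows unstratified → stratified.

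| Strata | Amyloid OR | Type I error, nominal 0.05 | Power, alpha 0.05 | Power, alpha 0.02774 |
|---|---|---|---|---|
| 6 | 1 | 0.048 → 0.049 | 99.1 → 99.1% | 98.2 → 98.1% |
| 6 | 3 | 0.039 → 0.048 | 99.5 → 99.7% | 98.8 → 99.4% |
| 6 | 10 | 0.020 → 0.048 | 99.8 → 100.0% | 99.5 → 100.0% |
| 9 | 1 | 0.049 → 0.050 | 98.9 → 98.9% | 98.1 → 98.2% |
| 9 | 3 | 0.043 → 0.051 | 99.1 → 99.4% | 98.5 → 98.9% |
| 9 | 10 | 0.030 → 0.051 | 99.4 → 99.9% | 98.9 → 99.8% |
| 18 | 1 | 0.045 → 0.045 | 98.9 → 98.9% | 98.0 → 98.1% |
| 18 | 3 | 0.045 → 0.050 | 99.2 → 99.5% | 98.4 → 98.8% |
| 18 | 10 | 0.035 → 0.051 | 99.6 → 99.8% | 99.2 → 99.7% |

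The gain is at most about 0.5 points at 0.05 and 0.9 points at 0.02774. With non-prognostic strata the differences are within simulation error, even with 18 strata.

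**5. If the effect falls short.** Take 60% of the planned difference at each visit. The donanemab rates become 3.0 + 0.6 × 32.7 = 22.6%, 22.8 + 0.6 × 27.3 = 39.2% and 27.8 + 0.6 × 26.8 = 43.9%. With 90 per arm, 6 strata and the slopes of step 3, power at 0.05 rises from 77–78% to 82–88%, a gain of roughly 5 to 10 points. Separately, with the planned rates but N = 100 and 5% loss per interval, power rises from about 89% to 91% (odds ratio 3) and from 90–93% to 96–98% (odds ratio 10).

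**The case against.** The strongest reply is that nothing is broken. The unstratified log-rank test is valid, any error is in the safe direction, and at the planned rates it already has about 99% power. All of that stands, and it is why the point is low priority.

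Three stronger readings are tempting, and the documents do not support them.

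- *The SAP contradicts its own Section 4.1.* That rule speaks of analysis models, and a log-rank test is not a regression model. The model for this endpoint, the Cox model, does include both factors. The text leaves the matter open; it does not conflict.
- *The p-value will be too large.* Conservatism is a property of the null distribution, not of every dataset, and it depends on how well the strata predict clearance. Because clearance means falling below a fixed 24.1 centiloids, a link with baseline amyloid is plausible. No passage quantifies it, and if it is absent there is no conservatism and no gain.
- *The gate is likely to fail here.* At the planned rates stratifying would rarely change the result of this test or of the one behind it.

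A practical objection is that Protocol 6.3 lets the sponsor discontinue or overenroll a stratum, and the number of amyloid levels is unstated, so sparse cells are possible. The simulations found no material cost with up to 18 strata, but the actual strata are unknown. This is a reason for a pooling rule, not for leaving the strata out.

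The Cox analysis answers the charge that adjustment is missing altogether. It does not settle the point, because the gated decision rests on the log-rank p-value.

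**Conclusion.** The point holds as a free improvement of low priority. The decisive test omits the randomization factors that every other co-primary and key secondary analysis includes. If the strata predict clearance as assumed (amyloid odds ratio 3 to 10, or slope 1.0 to 1.5 per SD), its actual type I error is about 0.02 to 0.045 at a nominal 0.05, while the stratified test stays close to nominal. The power gain is negligible under the planning assumptions and becomes material only if the effect or the sample falls well short of plan.

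These figures rest on assumed prognostic strength, stratum structure and later dropout, and on events placed at nominal visits. The SAP will use actual scan dates.

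**What to change.** In SAP 4.5.1.2, make the decisive comparison a log-rank test stratified by the randomization factors: amyloid stratum by ApoE ε4 status (noncarrier, heterozygous, homozygous). State the amyloid levels, and add a prespecified rule for pooling sparse strata that uses counts combined over the two arms. Keep the Kaplan-Meier curves unstratified and the Cox model as the sensitivity analysis.

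Record the change in SAP 4.10, which currently declares none, because Protocol 9.3.4.2 carries the same unstratified wording. Protocol 9.3.1 already allows a change that does not alter a principal feature to be described in the SAP and the clinical study report.

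The cost is a few sentences and a small programming change. No new data are needed, and neither the testing order nor the alpha changes. It should be settled before any unmasked time-to-clearance data are seen.

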4.5.1.3. Sensitivity Analyses

Observed values for mean changes in centiloid values will be reported for 6-, 12-, and 18- month PET scans. Additionally, a last-observation-carried-forward (LOCF) mean change analysis in centiloid values will be reported.

Time to plaque clearance will also be analyzed using a Cox proportional-hazards model with the treatment group as fixed effect variable of interest, and APOE e4 genotype, baseline amyloid levels, and baseline age as covariates.

4.5.1.4. Other secondary analyses

Mean percent change from baseline in brain amyloid plaque is defined as the specific time point PET centiloid value minus the baseline PET centiloid value, divided by the baseline PET centiloid value. These values will be modelled with the same approach as outlined for the mean change analyses.

Non-inferiority analyses will compare the changes in brain amyloid plaque levels for donanemab at 6 months to the changes in brain amyloid plaque levels for aducanumab at 12 months and at 18 months. The non-inferiority margin of interest is 5 centiloids. The MMRM models specified for the key secondary comparisons at 12 and 18 months will be used for the non-inferiority test, with appropriate contrasts and confidence intervals for the treatment-by-time interaction effects. For these non-inferiority analyses, if the upper bound of the 95% confidence interval for the donanemab vs. aducanumab contrasts is <5 centiloids, donanemab at 6 months will be considered to be non-inferior to aducanumab at that particular time point. An additional secondary objective to test the superiority of donanemab in amyloid plaque reduction at 6 months versus aducanumab at 12 months will also use this MMRM model and contrast.

For both the full study population and the intermediate tau subpopulation, the 12-month and 18-month comparison of proportion of participants with amyloid plaque clearance for donanemab versus aducanumab will include repeated post-baseline amyloid plaque clearance status (Yes/No) measurements and will be analyzed using separate generalized linear mixed model (PROC GLIMMIX) as pseudo-likelihood-based mixed effects repeated measures analysis assuming binomial distribution with a logit link. These models will be analyzed using data for outcomes up to and including the time point in question. The GLIMMIX model will include fixed effects for treatment, month, treatment-by-month interaction, APOE e4 genotype, baseline amyloid level, and baseline age as covariates. An unstructured variance-covariance matrix will be used to model the correlation among repeated measures on the same individual. If model convergence is not reached lesser restrictive variance-covariance structures will be employed until model convergence is attained.

For the mean change from baseline in amyloid plaque levels for the intermediate tau subpopulation, the statistical models will be identical to that of the full population, with analysis of covariance applied to the 6-month data and an MMRM analysis applied to the 12- and 18-month data.

4.6. Exploratory Endpoints Analysis and PK/PD Analyses

Exploratory biomarker samples are being collected throughout the study. These analyses will be performed in the overall study population and in the intermediate tau population. In addition to the analyses specified below, additional analyses of these data will be conducted as appropriate.

4.6.1. Analysis of Neurofilament Light Chain (NfL)

To evaluate the change from baseline in Neurofilament Light chain (NfL), an MMRM analysis will be used to compare change from baseline to scheduled collection times in the full analysis set. The model will include the fixed, categorical effects of treatment, visit, and treatment-by-visit interaction, as well as continuous effects of baseline NfL and age at baseline. Visit will be considered a categorical variable with values equal to the visit numbers at NfL is assessed. The null hypothesis is that the difference in means between donanemab and aducanumab equals zero. The values for NfL may be log transformed to fit the normality assumption of the model.

4.6.2. Analysis of Plasma Tau

To evaluate the change in plasma tau analytes (including assayed plasma total tau and p-tau) after treatment, an MMRM will be used to compare change from baseline to scheduled collection times in the full analysis set. The model will include the fixed, categorical effects of treatment, visit, and treatment-by-visit interaction, as well as the continuous effects of baseline plasma tau and baseline age. Visit will be considered a categorical variable with values equal to the visit numbers at which plasma tau is assessed. The null hypothesis is that the difference in means between donanemab and aducanumab equals zero.

4.6.3. PK/PD Analyses

Compartmental modeling of donanemab PK data using nonlinear mixed effects modeling or other appropriate methods may be explored, and population estimates for clearance and central volume of distribution may be reported. Depending on the model selected, other PK parameters may also be reported. Exploratory graphical analyses of the effect of dose level or demographic factors on PK parameters may be conducted. If appropriate, data from other studies of donanemab may be used in this analysis.

The PK/PD relationships between plasma donanemab concentration and florbetapir F18 PET parameters or other markers of PD activity may be explored graphically. The relationship between the presence of antibodies to donanemab and PK, PD, safety, and/or efficacy may be assessed graphically. If warranted, additional analysis may be explored to evaluate potential interactions for ADA, PD, and other endpoints (PET scan, safety, etc.).

